data at our institution suggests a rate closer to 12-15% for all symptomatic catheterrelated venous thrombosis (SVT and DVT). Some midline catheters are coated to provide protection against catheter-related venous thrombosis and/or catheterrelated bloodstream infection. The theoretical benefit(s) of these catheters need further validation in human subjects.

Objective

We aim to understand the difference in symptomatic catheter-related upper extremity venous thrombosis (CR-UEVT) comparing the Teleflex Arrowg+ard Blue Advance 4.5 F single lumen midline catheter to the AngioDynamics BioFlo 4 F single lumen midline catheter. Both catheters are inserted using a modified seldinger technique (MST). The AngioDynamics product has Endexo technology with claims of reduced platelet aggregation and favorable thrombus accumulation profile. The Teleflex catheter is a chlorhexidine coated device that claims to be both antithrombogenic and antimicrobial.

Specific Aim 1: To compare incidence of symptomatic CR-UEVT between the AngioDynamics Bioflo midline catheter and the Teleflex Arrowg+ard Blue Advance midline catheter.

For Aim 1, we will measure incidence of all symptomatic CR-UEVT inclusive of superficial thrombophlebitis (SVT) and deep venous thrombosis (DVT) confirmed by upper extremity venous doppler evaluation, to assess whether Arrowg+ard midline catheters offer a reduction in the incidence of symptomatic CR-UEVT.

Specific Aim 2: To compare incidence of catheter-related bloodstream infection between the AngioDynamics BioFlo midline catheter to the Teleflex Arrowg+ard Blue Advance midline catheter.

For Aim 2, we will identify cases of infection per the laboratory confirmed bloodstream infection criteria published by the Center for Disease Control (CDC), to assess whether Arrowg+ard Blue Advanced midline catheters offer reduction in catheter-related bloodstream infection.

Alternatively, for Aim 1 and Aim 2, to further examine the incidence of overall complications in the light of the differing catheter dwell times, catheter days data (including multiple insertions of midline catheters per patient in the study period) will be analyzed.

Specific Aim 3: To compare catheter survival rate data between the AngioDynamics BioFlo midline catheter and the Teleflex Arrowg+ard Blue Advance midline catheter.

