Sample Size: For this randomly allocated, two group experiment, the primary outcome was complication profile in terms of thrombophlebitis. Under Aim 1, based on the preliminary analysis using approximately 13 months of data at William Beaumont Hospital, it suggested the incidence of thrombosis between 12-15% from 1,200 insertions of AngioDynamics BioFlo midline catheters with the diagnosis of symptomatic thrombosis. We established a one-sided Fisher's exact twoproportions test with a type I error $\alpha = 0.05$. In terms of results from previous study [1], sample size was designed to have a power of 80% for detecting a 11% lower in the incidence of thrombosis using Teleflex Arrowg+ard Blue Advanced midline catheters. Based on these criteria, 212 participants will be randomly allocated to 2 study groups (106 per group). This sample size included a 20% buffer to account for potential sample loss. For Aim 3, this sample size has a power of 0.85 to detect a hazard ratio of 1.5 for failure of functionality association with AngioDynamics BioFlo midline catheters, based on a log rank test with a 0.05 one-sided significant level and median time of midline catheter introduction into a vein of 10 days [1]. All above calculations were made using the power software PASS 16.

Statistical Analysis: For Aim 1 and Aim 2, we will use descriptive statistics (frequency, percent) to summarize the incidence of complication profile in terms of thrombosis and infection between these two groups. For Aim 1, a logistic regression model will be built to examine the association between midline catheters and the presence of thrombosis, adjusting for participant characteristics. The odds ratio (OR) associated midline catheters on thrombosis will be estimated. For Aim 2, we will further create cases of bloodstream infection per 1000 catheter-days,

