accounting for catheter dwell times. A Poisson regression model will be employed to assess the relative risk (RR) of AngioDynamics BioFlo and Teleflex Arrowg+ard Blue Advanced midline catheters on the presence of infection within any observed catheter dwell time, adjusting for participant characteristics. P-values of less than 0.05 will be considered statistically significant. In addition, for Aim 3, we will create data with the first episode of function failure of catheter on IV treatment. To adjust for any difference in participant characteristics, Cox proportional hazard models will be built. We will evaluate the proportional hazard assumption for each fixed covariate of participant characteristics by the log baseline cumulative hazard plot, Schonfeld residual plot, and the interaction between the covariate and function time of midline catheters. If the assumption is violated, a stratified Cox proportional hazard model will be built. Hazard ratio (HR) of two midline catheters for function failure will be reported.

Site

William Beaumont Hospital, Royal Oak (RO) campus is a 1,100 bed major academic and referral center with Level 1 adult trauma and Level 2 pediatric trauma status. A major teaching facility, Beaumont, Royal Oak has 55 residency and fellowship programs with 454 residents and fellows. Beaumont is the exclusive clinical partner for the Oakland University William Beaumont School of Medicine. The Beaumont Research Institute was established more than 30 year ago at Royal Oak and offers research support services to clinical investigators.

Primary Investigator

I have specialized training in emergency ultrasound and completed fellowship in the field in 2008. Since that time, I have served as Director of Emergency Ultrasound for Emergency Medicine. I also serve as the Medical Director for the hospital vascular access team. Additionally, I have a specific interest in ultrasound-guided vascular access with several peer-reviewed publications and national presentations in this area.

References:

Lisova K et al. The incidence of symptomatic upper limb venous thrombosis associated with midline catheter: Prospective observation. Journal of Vascular Access. 2018. Epub ahead of print.

Klungboonkrong et al. Predictors of deep vein thrombosis associated with midline venous catheter in hospitalized patients: a single-institute experience. Journal of Vascular and Interventional Radiology 2015. 26(2) S146.

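### Aim 1 is sized on a one-sided Fisher's exact test that the analysis text does not carry forward; the adjusted logistic model planned there has no zero-event rule, and nothing says which result decides Aim 1

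*Combined protocol and SAP*

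**What the plan says.** The Sample Size paragraph, under Sample Size and Statistical Analysis, ties Aim 1 to a named test: "We established a one-sided Fisher's exact twoproportions test" at a type I error of 0.05. It asks for 80% power to detect an incidence 11% lower with Teleflex, from a BioFlo incidence of 12-15%, and arrives at 212 participants, 106 per group. On attrition it adds: "This sample size included a 20% buffer to account for potential sample loss". Aim 3 is also powered one-sided at 0.05.

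The Statistical Analysis paragraph then reads differently. It opens with "For Aim 1 and Aim 2, we will use descriptive statistics (frequency, percent) to summarize the incidence of complication profile", continues for Aim 1 with "a logistic regression model will be built to examine the association between midline catheters and the presence of thrombosis, adjusting for participant characteristics", and adds "The odds ratio (OR) associated midline catheters on thrombosis will be estimated". The only significance rule is "P-values of less than 0.05 will be considered statistically significant"; it follows the Aim 2 Poisson model and gives no side. Specific Aim 1, under Objective, is directional: "to assess whether Arrowg+ard midline catheters offer a reduction in the incidence of symptomatic CR-UEVT".

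Initial Assessment lists age, gender, BMI, vital signs and ten history items as data to collect. None is designated as a model covariate.

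**The concern.** A power statement is informative only for the test that will decide the question. Here the test used for sizing and the analysis described are different procedures, and the plan does not say which governs. With few events they can disagree. The sharpest case is an arm with no thromboses. That would be the best possible result for Teleflex, yet an ordinary maximum-likelihood logistic fit then yields no finite odds ratio and a Wald test that cannot reject.

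At stake is the primary result. If the deciding test, its statistic and its covariates are not fixed beforehand, they can be chosen once the data are known, and the promised odds ratio may not exist.

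**Working it through.** **Inputs.** From the Sample Size paragraph: one-sided alpha 0.05, power 80%, BioFlo incidence 12-15%, 11% lower with Teleflex, 106 per arm including 20% for loss. Two assumptions are needed. The plan does not give the single BioFlo rate it used, so I take values across 12-15%. I read the 11% as percentage points, because an 11% relative reduction would give only 6-7% power with 106 per arm.

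**Reproducing the plan's figure.** Exact one-sided Fisher power (binomial sampling, all 2x2 tables) first reaches 80% at these sizes per arm:

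- 12 v 1%: 69; 69/0.8 gives 87 after rounding up.
- 13.5 v 2.5%: 83; 83/0.8 gives 104.
- 14 v 3%: 89; 89/0.8 gives 112, or 89 x 1.2 gives 107.
- 15 v 4%: 99; 99/0.8 gives 124.

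The stated 106 sits near the middle of the range, so the sizing is sound for the test it names.

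**Evaluable numbers after full 20% loss.** 106 x 0.8 = 84.8, about 85 per arm; 106/1.2 = 88.3, about 88 per arm. Both are carried.

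**Expected events** = n x (sum of the two rates). Lowest: 85 x (0.12 + 0.01) = 11.1. Highest: 88 x (0.15 + 0.04) = 16.7. With no loss: 106 x 0.13 = 13.8 to 106 x 0.19 = 20.1.

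**Chance of zero Teleflex events** = (1 - p)^n. For example, 0.975^85 = 0.116 and 0.99^85 = 0.426.

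**Unadjusted one-sided power**, by enumerating every table, 85-88 per arm. Wald counts a zero-event table as a non-rejection.

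| BioFlo v Teleflex | P(zero Teleflex events) | Fisher | Wald | Likelihood ratio |
|---|---|---|---|---|
| 15 v 4% | 3% | 73-75% | 77-79% | 83% |
| 14 v 3% | 7-8% | 78-80% | 76-78% | 87-88% |
| 13.5 v 2.5% | 11-12% | 81-83% | 74-76% | 89-90% |
| 12 v 1% | 41-43% | 90-91% | 51-53% | 96% |

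With no loss (106 per arm), the chance of zero Teleflex events is 1, 4, 7 and 34% in the same order.

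**Where the tests part.** Comparing one-sided Fisher and Wald table by table, Fisher rejects and Wald does not only when Teleflex has zero events and BioFlo at least 5. Example: 0/88 v 10/88 gives one-sided Fisher P = 0.0007. The maximum-likelihood odds ratio is not finite. The Firth estimate is (0.5/88.5)/(10.5/78.5) = 0.04.

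**If the 0.05 threshold is read as two-sided**, power at 13.5 v 2.5% is 71-73% for Fisher and 63-66% for Wald.

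**An example without a zero cell.** At 3/88 v 10/88, one-sided Fisher gives P = 0.040, two-sided Fisher 0.080 and two-sided Wald 0.057. The conclusion turns on a choice that the analysis text leaves open.

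**The case against.** The best defence is that the sizing sentence sits under a joint heading for sample size and analysis and can be read as naming the Aim 1 test, with the logistic model as an adjusted supplement. That reading is possible. What the text shows is narrower: the analysis paragraph does not repeat Fisher's test or rank it against the model.

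The side of the test is also less open than the bare 0.05 threshold suggests. Aims 1 and 3 are both sized one-sided, and the aims are worded directionally. A reader might infer that a two-sided test is planned and that power drops accordingly; no passage says so, and the two-sided figures are only a contingency.

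The one-sided Wald deficit depends on how zero-event tables are scored. If those that Fisher rejects were counted as rejections, Wald power at 13.5 v 2.5% would be 86-87%, above Fisher. At 15 v 4% Wald already exceeds Fisher. This stands, and it places the defect in the missing zero-event rule rather than in logistic regression as such.

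The event count of 11-17 assumes both the full loss and the planned benefit. With no loss it is 14-20. With 12-15% in both arms, 170-176 patients would give about 20-26. Follow-up Assessment has all subjects' records screened for Doppler examinations, so full loss of the primary outcome is not certain.

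Finally, a reader might infer that adjusting for every recorded characteristic would wreck the analysis. The plan does not say all would be entered. In a simulation with 13 covariates unrelated to thrombosis, power was essentially unchanged, and the two-sided likelihood-ratio type I error rose to about 6-7.5%. The covariate prevalences and null effects were assumed, so this is weak evidence of harm; it supports only naming a short list in advance.

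**Conclusion.** The point holds as an under-specified primary analysis with one concrete failure mode. The 80% power belongs to a test that the analysis text does not carry forward. The model described there, fitted by ordinary maximum likelihood, can fail to give an odds ratio: a 3-12% chance at three of the four rate pairs and 41-43% at 12 v 1%, with 85-88 evaluable per arm. On the one-sided reading at 13.5 v 2.5%, power is 81-83% by Fisher, 74-76% by Wald and 89-90% by likelihood ratio.

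A reader might infer that the trial is underpowered. The documents do not support that: 106 per arm fits the named test near mid-range, and the alternatives move power both ways. Fisher's value below 80% at 15 v 4% comes from the width of the planning range, not from a change of test.

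The figures assume an 11-point difference, BioFlo rates within 12-15%, and no covariate effects. The omission is certain from the text; the size of its consequence depends on the true rates. It should be fixed before the data are analysed.

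**What to change.** 1. State that the primary Aim 1 analysis is the one-sided Fisher's exact test at 0.05 used for sizing, reported with the risk difference and an exact or score confidence interval. Label the adjusted odds ratio as supportive.
2. Fit the logistic model by Firth penalised likelihood, or by exact logistic regression, with a short covariate list named in advance, so that an odds ratio is available even with no events in one arm.
3. If two-sided testing or a model-based primary test is intended, say so and restate the power. Two-sided Fisher with 85-88 per arm gives 63-65% at 15 v 4%, 68-70% at 14 v 3%, 71-73% at 13.5 v 2.5% and 81-83% at 12 v 1%. A one-sided Firth likelihood-ratio test, unadjusted, gives 80-82, 85-86, 87-88 and 94-95% in the same order.

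The cost is SAP wording, plus one power rerun under item 3. Enrolment and procedures do not change under items 1 and 2. The downsides are that the adjusted odds ratio no longer decides Aim 1, and that Fisher's test is conservative: its actual one-sided type I error is about 3.0-3.2% at 12-15% incidence with 85-88 per arm.

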For Aim 3, an improved survival of Arrowg+ard Blue Advanced midline catheters will be evaluated by functionality of catheter for intravenous therapy prior to patient discharge. The event is failure of functionality identified during follow-up assessment during hospitalization. Duration of dwell and functional failure of the catheter will be employed to estimate catheter survival.

Study Design

We propose a prospective single-site, parallel, two-arm, randomized investigation to assess catheter-related symptomatic UEVT, catheter-related bloodstream infection, and functionality of two single lumen midline catheters: AngioDynamics BioFlo 4 F and Teleflex Arrowg+ard Blue Advance 4.5 F. The research protocol was approved by the Institutional Review Board of Beaumont Research Institute. Written informed consent will be obtained from all participants.

All inpatients 18 years of age and older that require midline catheter placement by the bedside vascular access team will be eligible participants. Patients will be excluded if: Do not meet inclusion criteria 2. Multiple lumens required 3. Alternative diameter of catheter used 4. If already enrolled once prior 5. Withdraw voluntarily from the study 6. Are receiving oral, intravenous, or subcutaneous treatment dose anticoagulation (prophylaxis with anticoagulant is permissible).

Research staff of Beaumont Health Institute will allocate two midline catheters to eligible participants according to a pre-generated randomized list at a 1:1 ratio in block randomization to AngioDynamics BioFlo or Teleflex Arrowg+ard Blue Advanced midline catheters. Participant enrollment will take place from November 2018 until patient recruitment is complete. Demographic and health-related information will be obtained from electronic medical records during enrolled period at William Beaumont Hospital.

Practitioner Participation/Training

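### Aim 2 rests on a covariate-adjusted Poisson model with no expected infection count and no rule for sparse data; an unadjusted exact rate comparison, labelled descriptive, should be the main analysis

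*Combined protocol and SAP*

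**What the plan says.** Under Sample Size and Statistical Analysis, the Statistical Analysis text for Aim 2 has three layers. Infections are summarised by arm as frequency and percent. They are then put on an exposure scale: "we will further create cases of bloodstream infection per 1000 catheter-days". Finally, "A Poisson regression model will be employed to assess the relative risk (RR") for the two catheters, with adjustment for participant characteristics that are not listed. The significance threshold is 0.05, and sidedness is not stated for Aim 2.

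The Sample Size paragraph is built on thrombosis, with a further power statement for Aim 3: "sample size was designed to have a power of 80% for detecting a 11% lower in the incidence of thrombosis", leading to "212 participants will be randomly allocated to 2 study groups (106 per group"). It gives no infection rate, infection count or power for Aim 2. The only figure from which exposure can be gauged is the one used for Aim 3, a "median time of midline catheter introduction into a vein of 10 days", taken from a cited study. The Objective section adds that catheter-days may include several insertions in one patient.

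**The concern.** A rate ratio from an unpenalised Poisson model is finite only if both arms have at least one event. A trial sized for an outcome expected in 12-15% of the BioFlo arm may produce very few bloodstream infections, and the plan does not say what happens then. The risk of an empty arm rises if the Arrowg+ard catheter reduces infection, which is what Aim 2 sets out to assess.

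Two errors could follow. A strong imbalance with a zero arm could be reported as clearly non-significant, because the Wald standard error becomes enormous. Or an uninformative non-significant P could be read as showing equal infection risk.

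**Working it through.** **The plan's own figure.** With a one-sided Fisher exact test at 0.05, 80% power and a difference of 11 points from the midpoint of 12-15% (13.5% v 2.5%), 83 per arm are needed. Allowing for 20% loss, 83/0.8 = 103.75, so 104 per arm against the stated 106. The patient count is therefore close to its stated basis, and that basis is thrombosis only.

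**Catheter-days.** No total is given, so a range is used.
- All 212 patients x 10 days = 2,120.
- After the loss buffer ("This sample size included a 20% buffer to account for potential sample loss"), 212 x 0.8 is about 170, and 170 x 10 = 1,700.
- Ten days is a median. If dwell were exponential, the mean would be 10/ln 2 = 14.4 days, and 212 x 14.4 is about 3,060.

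Repeat insertions would add to each figure.

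**Infection rate.** The documents give none. Rates of 0.5, 1, 2 and 5 per 1000 catheter-days in the BioFlo arm are assumed.

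**Chance of a zero arm.** With 1:1 allocation and equal exposure, BioFlo infections are Poisson with mean m1 = rate x 2,120/2000, and Arrowg+ard infections have mean m2 = RR x m1. Then P(at least one arm has none) = exp(-m1) + exp(-m2) - exp(-m1-m2). For example, at 1 per 1000 with equal rates, m1 = m2 = 1.06 and 2 x 0.346 - 0.120 = 0.57.

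| Assumed rate per 1000 days | Expected infections, RR 1 | P(zero arm), RR 1 | P(zero arm), RR 0.5 |
|---|---|---|---|
| 0.5 | 1.1 | 83% | 90% |
| 1 | 2.1 | 57% | 73% |
| 2 | 4.2 | 23% | 43% |
| 5 | 10.6 | 1% | 8% |

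Exposure matters too. At 2 per 1000 with equal rates, the chance is 33% at 1,700 days and 9% at about 3,060. At 2,120 days it exceeds one half only below about 1.2 per 1000 (RR 1) or 1.7 (RR 0.5). Over the whole exposure range those cut-offs are 0.8-1.4 and 1.2-2.1.

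**Covariates.** The list is not given, so six binary covariates with prevalence 10-50% were assumed and 400 trials simulated per rate. Some coefficient was non-finite in 100%, 98%, 89% and 55% of trials at the four rates. The catheter coefficient itself was non-finite in 83%, 57%, 26% and 1%, almost the same as the zero-arm chance.

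**What the model reports with a zero arm.** Equal dwell, 8 v 0, unadjusted Poisson fit: RR about 2e-10, standard error about 15,600, Wald P about 0.999. The exact conditional two-sided P is 2 x 0.5^8 = 0.008. For 6 v 0, Wald P is again 0.999, against an exact 2 x 0.5^6 = 0.031.

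**What an exact test can show.** With equal exposure, n v 0 gives a one-sided P of 0.5^n. The ordinary exact test therefore reaches 0.05 at 5 v 0 one-sided (0.031) or 6 v 0 two-sided (0.031). Mid-P halves these values, so it needs 4 v 0 or 5 v 0. At 2,120 days, two-sided power of the ordinary exact test for RR 0.5 is about 0.01 at 2 per 1000, 0.08 at 5 and 0.19 at 10.

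**The case against.** Aim 2 is not the primary outcome, and counts, percentages and rates per 1000 catheter-days will be reported whatever the model does. This stands, and it limits the harm: some interpretable output survives a failed fit.

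The plan does not name Wald tests, so likelihood-ratio inference would also fit the text. That is true, but it does not settle the matter. With equal exposure and n v 0, the likelihood-ratio statistic is 2n ln 2. For 3 v 0 it is 4.16 on 1 df, P about 0.04, where the exact two-sided P is 2 x 0.5^3 = 0.25. Large-sample inference is unreliable at these counts in either form.

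A reader might infer that the Poisson RR will usually be inestimable. The documents do not support this, because they give no infection rate. At 2 per 1000, about four infections, the catheter RR is finite in roughly three trials in four under equal rates. At 5 per 1000, failure is rare.

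A reader might also infer that sparse covariates make the catheter RR inestimable. A covariate level without infections sends its own coefficient to infinity but does not by itself remove the catheter RR. The covariate set is also unknown: age and BMI are collected as well, and continuous variables have no empty levels.

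Finally, it can be said that an exact test has little power. It does. The argument for it is validity with a zero arm, not a better chance of significance.

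**Conclusion.** The concern holds as a gap in the plan for a likely situation. Over an assumed 0.5-2 infections per 1000 days and 1,700-3,060 catheter-days, about 1 to 6 infections are expected under equal rates. At 2,120 days, the chance of an empty arm runs from 83% down to 23% under equal rates, and from 90% to 43% if the true RR is 0.5. In those trials the planned RR has no finite estimate and its usual P value is misleading.

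These figures depend on the assumed infection rate, on a median dwell standing in for a mean, on equal exposure by arm and on no repeat insertions. They do not show that the model fails at every plausible rate. They do show that it should not be the only planned comparison.

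**What to change.** In the Aim 2 part of the Statistical Analysis text:

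1. Make the main comparison an unadjusted exact conditional (binomial) test of infections per catheter-day, with an exact interval for the rate ratio. Given the total number of infections, the reference proportion is each arm's share of catheter-days.
2. State whether it is one- or two-sided, and whether the ordinary exact or the mid-P version is used, since the thresholds differ.
3. Count the first infection per patient, or otherwise handle repeat insertions in the same patient, because the exact test treats infections as independent.
4. Keep any adjusted Poisson model as secondary, Firth-penalised and limited to very few covariates named in advance.
5. State the assumed infection rate and the expected count. Label Aim 2 descriptive, and say that a non-significant result is not evidence of equal risk.

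The cost is a change of SAP wording. Covariate adjustment is given up in the main Aim 2 comparison, which is a modest loss when patients are allocated "at a 1:1 ratio in block randomization". Power remains low, about 0.08 two-sided for RR 0.5 at 5 per 1000 days, so the gain is a valid P value and an honest interval.
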